#### REGULATORY

- 3.2.11 All patients and/or their parents or legal guardians must sign a written informed consent.
- 3.2.12 All institutional, FDA, and NCI requirements for human studies must be met.

## 4.0 TREATMENT PLAN

## 4.1 **Overview of Treatment plan**

Timing of protocol therapy administration, response assessment studies, and surgical interventions are based on schedules derived from the experimental design or on established standards of care. Minor unavoidable departures (up to 72 hours) from protocol directed therapy and/or disease evaluations (and up to 1 week for surgery) for valid clinical, patient and family logistical, or facility, procedure and/or anesthesia scheduling issues are acceptable per COG administrative Policy 5.14 (except where explicitly prohibited within the protocol).

In this study, patients will be randomized to no levofloxacin (Arm A) or levofloxacin (Arm B) at time of enrollment. Patients in Arm A receive no protocol treatment. Patients in Arm B receive levofloxacin as detailed below.

The required observations and adverse event reporting are identical in the two arms. See Section 7 for required observations and Section 11 for Adverse Event reporting.

## 4.1.1 Levofloxacin Treatment

Patients with AL

For children with AL and assigned to Arm B, prophylaxis will be administered during 2 consecutive cycles of chemotherapy; levofloxacin will start on Day 3 of systemic therapy for each of the 2 consecutive chemotherapy cycles.

## Patients Undergoing HSCT

For children undergoing HSCT and assigned to Arm B, prophylaxis will be administered during 1 transplant procedure; levofloxacin will start on Day -2 from stem cell infusion.

For patients with AL and those undergoing HSCT, levofloxacin treatment will continue until one of the following is met, whichever occurs first:

- 1) ANC is  $> 200/\mu L$  and rising post-nadir OR
- 2) Day 60 (from Day 1 of each cycle of systemic chemotherapy or HSCT Day +60) if  $ANC > 200/\mu L$  is not reached OR
- 3) The day prior to the next cycle of chemotherapy OR
- 4) Patient meets criteria for removal from protocol therapy per Section 8.1.

For patients with AL receiving 2 courses of levofloxacin treatment, the first course of levofloxacin treatment will be discontinued when the patient meets the above criteria; unless the patient is off protocol, the second course of levofloxacin treatment will start on Day 3 of the next chemotherapy cycle. Patients who begin their second cycle of chemotherapy before the ANC >  $200/\mu L$  and before Day 60 (for Cycle 1) should continue levofloxacin treatment until the ANC is >  $200/\mu L$  and rising post nadir or they reach 60 days from Day 1 of the second cycle of chemotherapy.

For patients assigned to Arm B, levofloxacin will be held any time that parenteral antibacterial therapy is initiated according to local supportive care standards (for example, empiric antibiotics initiated for febrile neutropenia). For patients who have not met criteria for removal from protocol therapy, levofloxacin should be re-started when parenteral antibiotics have been discontinued (for example, following completion of a 14-day course of empiric therapy for febrile neutropenia), if the ANC is still  $< 200/\mu L$ , if Day 60 has not yet been reached and the next cycle of chemotherapy has not been initiated. For HSCT patients who develop fever between the time of enrollment and Day -2 of

conditioning (for example fevers associated with ATG therapy) who are started on empiric antibiotic therapy according to institutional standards, levofloxacin should be started once these empiric antibiotics are discontinued or on Day -2 of conditioning, whichever occurs later. Levofloxacin may be stopped and re-started multiple times according to when other parenteral antibiotics are administered.

Levofloxacin should be discontinued immediately for any patient with confirmed tendinopathy (tendonitis or tendon rupture).

**Please note:** For all patients on study (i.e., Arms A and B), decisions regarding the initiation and choice of empiric and treatment antimicrobial therapy should be made according to local supportive care standards.

For COG Supportive Care Guidelines see

https://members.childrensoncologygroup.org/prot/reference materials.asp

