#### See Section 5.0 for Dose Modifications based on Toxicities.

The therapy delivery maps (TDMs) for levofloxacin therapy are on the next 2 pages.

Prophylactic Therapy Delivery Map – AL Patients in Arm B	
Patients undergoing treatment for AL receive antibacterial prophylaxis during 2 consecutive cycles	
of chemotherapy.	Patient name or initials
	DOD

For each of 2 consecutive chemotherapy cycles, begin study treatment on Day 3 of systemic chemotherapy. Extensive details are in Section 4.0 (treatment overview). Cvcle: 1

This Therapy Delivery Map is on **one** (1) page.

		(-) F8-1		-,	
DRUG	ROUTE	DOSAGE	DAYS	IMPORTANT NOTES	OBSERVATIONS
Levofloxacin	PO*/IV  *Given PO if tolerated; otherwise by IV.	Age ≥ 6 months to < 5 years: 10 mg/kg twice daily ≥ 5 yrs: 10 mg/kg once daily	Daily beginning on Day 3 of systemic chemotherapy)^	^Continue until ANC is > 200/μL and rising post-nadir or Day 60 (from Day 1 of each cycle of systemic chemotherapy) if ANC > 200/μL is not reached or the day prior to the next cycle of chemotherapy.  Note age-based dosing	
 
a. History, physical, ht/wt, performance status
 
b. CBC, Cr (at intervals according to good patient care)
 
c. Optional peri-rectal swab or stool specimen (see Section 7.2)
 
† Infection information during infection observation period (see Section 7.1.2)
 

				Maximum per day: 500 mg if < 5 years of age, 750 mg if ≥ 5 years See Section 4.2 for rounding of oral doses	OBTAIN OTHER STUDIES AS REQUIRED FOR GOOD PATIENT CARE

		Htcr	n Wtkg	BSA	$_{\rm m}^2$	
Start Day	Stop Day Date	Age: $\geq$ 6 months to $\leq$ 5 years	Age: $\geq 5$ years	Studies †	Comments (Include any held doses, or dose modifications)	
Date (d/m/y)	(d/m/y)	LEVO^	LEVO^			
` **	• • • • • • • • • • • • • • • • • • • •	mgmg	mg			
		Enter calculated dose above an	d actual dose administered b	oelow		
0-3				a, b, c		
3 ( / / )	(_/_/)^	mgmg	mg			
(_/_/)	(_/_/)^	mgmg	mg			
(_/_/)	(_/_/)^	mgmg	mg			
(_/_/)	(_/_/)^	mgmg	mg			
Continue until ANC is > 200/uL and rising post-padir  ; see Section 4.1 for details regarding starting and stopping of levofloxacin						

Continue until ANC is  $> 200/\mu$ L and rising post-nadir'; see Section 4.1 for details regarding starting and stopping of levofloxacin. Levofloxacin should be discontinued immediately for any patient with confirmed tendinopathy (tendinitis or tendon rupture) (see Section 4.1).

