On the TDM, indicate each start and stop dates of levofloxacin. The subject may start and stop levofloxacin multiple times prior to meeting the criteria for completion of levofloxacin. Levofloxacin should be held when parenteral antibiotics are administered for other indications such as for empiric or therapeutic management of infection.

See Section 5.0 for Dose Modifications for Toxicities and the COG Website posted materials for Supportive Care Guidelines

Prophylactic Therapy Delivery Map – HSCT Patients in Arm B	
Patients undergoing HSCT receive antibacterial prophylaxis during 1 transplant procedure.	Patient name or initials
	DOB

Begin study treatment on Day -2 from stem cell infusion. Extensive details are in Section 4.0 (treatment overview).

This Therapy Delivery Map is on one (1) page.

DRUG	ROUTE	DOSAGE	DAYS	IMPORTANT NOTES	OBSERVATIONS
Levofloxacin	PO*/IV	Age	Daily beginning on	^Continue until ANC is $> 200/\mu L$	a. History, physical, ht/wt, BSA, performance
		$\geq$ 6 months to $\leq$ 5 years:	Day -2^	and rising post-nadir or HSCT	status
	*Given PO if	10 mg/kg twice daily		Day +60 if ANC > $200/\mu$ L is not	b.CBC, Cr (at intervals according to good
	tolerated;			reached	patient care)
	otherwise by IV.	≥ 5 yrs: 10 mg/kg once daily		Note age-based dosing	c. Optional peri-rectal swab or stool specimen (see Section 7.2)
				Maximum per day: 500  mg if < 5  years of age, $750 \text{ mg if} \ge 5 \text{ years}$	† Infection information during infection observation period (see Section 7.1.2)
				See Section 4.2 for rounding of oral doses	OBTAIN OTHER STUDIES AS REQUIRED FOR GOOD PATIENT CARE

		Ht	_cm	Wtkg	BSA	$m^2$
Start Day	Stop Day Date	Age: $\geq$ 6 months to	< 5 years	Age: ≥ 5 years	Studies †	Comments (Include any held doses, or dose modifications)
Date (d/m/y)	(d/m/y)	LEVO^		LEVO^		
` • •		mg	mg	mg		
		Enter calculated dos	e above and	actual dose administered	l below	
-3					a, b, c	
-2 # (_ /_ /)	_ (_ /_ /)^	mg	mg	mg		
	_ (_ /_ /)^	mg	mg	mg		
	_ (_ /_ /)^	mg	mg	mg		
(_/_/)	_ (_ /_ /)^	mg	mg	mg		
	Continue until ANC is $> 200/\mu$ L and rising post-nadir ^ ; see Section 4.1 for details regarding starting and stopping of levofloxacin.					
	Levofloxacin should be discontinued immediately for any patient with confirmed tendinopathy (tendinitis or tendon rupture) (see Section 4.1).					

#Stem cell infusion 2 days later on Day 0

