# 7.1.2 Infection Observation Period and Infection Information

The observation period for infectious outcomes, including the primary endpoint will be the same for both arms irrespective of whether the child discontinues levofloxacin early for those allocated to that arm. Specifically for patients receiving chemotherapy, the infection observation period will begin Day 3 of each cycle of chemotherapy and will end when the ANC is  $> 200/\mu L$  and rising post nadir, or at Day 60 (from Day 1 of each cycle of systemic chemotherapy) if an ANC of  $> 200/\mu L$  has not been reached, or Day 1 of the next cycle of chemotherapy, whichever occurs first. For patients undergoing HSCT, the observation period will begin on Day -2 from stem cell infusion and end when the ANC is  $> 200/\mu L$  and

<sup>2 To be done at intervals according to good patient care.

<sup>3 See Section 7.2. for collection details and Section 13.0 for shipping details.

rising post nadir, or at HSCT Day +60 if an ANC >  $200/\mu$ L has not been reached or the first day of subsequent cancer therapy, whichever occurs first.

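### Section 4.1.1: the ANC condition for restarting levofloxacin after parenteral antibiotics does not match the stop rule, so a patient whose antibiotics end before the nadir with ANC at or above 200/µL meets neither

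*Combined protocol and SAP*

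**What the plan says.** Section 4.1.1 sets a general rule for both AL and HSCT patients in Arm B: "levofloxacin treatment will continue until one of the following is met, whichever occurs first". The four criteria are ANC above 200/µL and rising post-nadir, Day 60, the day before the next chemotherapy cycle, and removal under Section 8.1.

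The drug is held whenever parenteral antibacterial therapy begins, whatever the ANC. For patients not removed from protocol therapy, "levofloxacin should be re-started when parenteral antibiotics have been discontinued", subject to three conditions: "if the ANC is still $< 200/\mu L$ , if Day 60 has not yet been reached", and the next cycle has not started. The sentence mentions neither the nadir nor the direction of the ANC.

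Three other statements bear on restarting:

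- Section 4.1.1: "Levofloxacin may be stopped and re-started multiple times according to when other parenteral antibiotics are administered".
- Section 4.1.1, for HSCT patients given empiric antibiotics for fever before Day -2: "levofloxacin should be started once these empiric antibiotics are discontinued or on Day -2 of conditioning, whichever occurs later". This has no ANC test, but it governs the first start only.
- The therapy delivery maps in Section 4.2: "The subject may start and stop levofloxacin multiple times prior to meeting the criteria for completion of levofloxacin". The maps repeat the ANC stop rule and then send the reader back: "see Section 4.1 for details regarding starting and stopping of levofloxacin".

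Section 7.1.2 makes follow-up independent of exposure: "The observation period for infectious outcomes, including the primary endpoint will be the same for both arms irrespective of whether the child discontinues levofloxacin early". Section 9.3.3 specifies intent-to-treat for the primary analyses of treatment effect.

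**The concern.** A restart rule after a temporary hold should be the complement of the stop rule: if the patient has not finished, resume. Here it is not. The stop rule needs three things together (ANC above 200/µL, rising, post-nadir), while the restart rule looks only at whether the ANC is below 200/µL. The ANC clause stands beside two limits, Day 60 and the next cycle, that are plainly necessary conditions, so reading it as necessary too is reasonable.

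The state can arise because levofloxacin starts by calendar day (Day 3 of the cycle for AL, Day -2 for HSCT), when the ANC may still be above 200/µL. A short parenteral course begun after that and ended before the nadir puts the patient in the gap. Under a literal reading, the patient could pass through that cycle's neutropenia without prophylaxis, which is the period the primary objective addresses, while still counting in Arm B. Sites could also treat identical patients differently.

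**Working it through.** **1. Do the two rules match?** Take nadir status (pre, post), direction (rising or not) and ANC of 150, 200 or 250/µL. Apply the ANC part of each rule, with the other limits not yet reached.

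| State | ANC 150 | ANC 200 | ANC 250 |
|---|---|---|---|
| Pre-nadir, not rising | restart | neither | neither |
| Pre-nadir, rising | restart | neither | neither |
| Post-nadir, not rising | restart | neither | neither |
| Post-nadir, rising | restart | neither | stop |

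Of 12 combinations, 4 allow restart, 1 meets the stop rule and 7 meet neither. Four of the 7 are pre-nadir, which is the case at issue. No combination meets both rules.

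**2. Baseline power (Section 9.3.2).** For a two-sided chi-square test at 0.05 with n per arm,

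power = Φ{ [ |p1 − p2|·√n − 1.96·√(2·p̄(1 − p̄)) ] / √[ p1(1 − p1) + p2(1 − p2) ] }, where p̄ = (p1 + p2)/2.

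- HSCT, 200 per arm, 20% vs 10%: Φ(0.4245/0.5000) = Φ(0.849) = 80.2%. The plan states 80%.
- AL, 133 per arm, 30% vs 15%: Φ(0.5724/0.5809) = Φ(0.985) = 83.8%. The plan states about 84%.

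Both stated figures reproduce.

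**3. Effect of undelivered drug.** The affected fraction f of Arm B is not in the documents, so f = 1%, 2% and 5% are assumptions, as is the share of effect lost.

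*HSCT, half the effect lost.* An affected patient's risk is 15%, so the Arm B rate is 0.10(1 − f) + 0.15f.

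*AL, one of two cycles without effect.* Assume equal, independent cycle risks. The per-cycle risk is 1 − √0.70 = 16.3% in control and 1 − √0.85 = 7.8% in Arm B. An affected patient's risk is 1 − (1 − 0.1633)(1 − 0.0780) = 22.9%, so the Arm B rate is 0.15 + 0.0786f. The loss is confined to one cycle because drug starts again on Day 3 of the next.

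| f | HSCT Arm B rate | HSCT power | AL Arm B rate | AL power |
|---|---|---|---|---|
| 0 | 10.00% | 80.2% | 15.00% | 83.8% |
| 1% | 10.05% | 79.8% | 15.08% | 83.3% |
| 2% | 10.10% | 79.3% | 15.16% | 82.9% |
| 5% | 10.25% | 77.9% | 15.39% | 81.5% |

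At f = 2% the affected patients number 200 × 0.02 = 4 (HSCT) and 133 × 0.02 ≈ 3 (AL). The expected extra patients with bacteremia are 200 × 0.02 × 0.05 = 0.2 and 133 × 0.02 × 0.0786 ≈ 0.2.

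**4. Range for the assumed loss.** If affected HSCT patients lost the whole effect, the Arm B rate would be 10.1%, 10.2% and 10.5%, and power 79.3%, 78.4% and 75.4%. If AL patients lost only half of one cycle's effect (affected risk 18.9%), power would be 83.6%, 83.3% and 82.7%.

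**The case against.** The best answer is that the general rule already covers the case. Treatment continues until a stop criterion is met, and this patient has met none. Antibiotics cause a hold, not a discontinuation. The restart sentence says *if*, not *only if*, and nothing forbids restarting at ANC 200/µL or above. The delivery maps, where sites record start and stop dates, frame restarts by the completion criteria. The sentence can also be read as a continuing condition: once the ANC falls below 200/µL with antibiotics off, every condition is satisfied and drug resumes, with only the days above 200/µL lost.

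The group is narrow too. Patients already on non-exempt antibacterials are ineligible (Section 3.2.10), HSCT fever before Day -2 has its own start rule, and the sentence's own example, a 14-day febrile-neutropenia course, concerns patients who are already neutropenic.

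Most of this stands, and it limits the point to sites that apply the clause literally. It does not remove the mismatch. The permissive statements set no restart test, the maps defer to Section 4.1 for starting and stopping, and the word *still* leaves open whether the ANC is tested once or repeatedly.

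A reader might infer more: that the protocol requires levofloxacin to be withheld through the nadir, or that the primary comparison is compromised. The documents support neither. The pre-Day -2 rule shows that dosing before the nadir is intended, and the common observation period and intent-to-treat analysis are the right choices.

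**Conclusion.** The point holds as a low-severity inconsistency between two stated rules. It has consequences only where a site reads the restart sentence literally, and drug is missed through the nadir only if that site also fails to revisit the ANC. The result would be avoidable under-delivery of prophylaxis in a small group of unknown size, diluting the comparison slightly toward no difference. It would not favor levofloxacin.

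At f = 2%, the loss is about 0.9 power points in each cohort (80.2% to 79.3% for HSCT, 83.8% to 82.9% for AL). This rests on an assumed affected fraction, an assumed share of effect lost and, for AL, equal independent cycle risks. It shows scale and is not an estimate. It gives no reason to change the sample size, and no figure in Section 9.3.2 is wrong.

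**What to change.** In the restart sentence of Section 4.1.1, replace the ANC condition with: *unless any stop criterion in Section 4.1.1 has already been met in that cycle, including during the antibiotic course*. Keep the Day 60 and next-cycle limits, and put the same wording in the AL and HSCT therapy delivery maps.

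This restarts the pre-nadir patient. It does not restart a patient who met the recovery criterion during antibiotics and whose ANC later plateaued or dipped.

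The cost is a wording amendment with a memo to sites, and slightly more levofloxacin exposure in a few patients. It needs no added patients, visits or data.

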#### 4.1.2 Prophylactic Therapy

Antibacterial prophylaxis other than for PCP prophylaxis and levofloxacin for those on Arm B will not be permitted.

# 4.2 **Study Therapy**

## **Levofloxacin: PO\* or IV**

Age  $\geq 6$  months to  $\leq 5$  years: administer 10 mg/kg twice daily for a total of 20 mg/kg per day

Maximum: 250 mg per dose; 500 mg per day

Age  $\geq$  5 years: administer 10 mg/kg once daily

Maximum: 750 mg per day

\*The study medication will be given PO if tolerated. If PO is not tolerated, study medication will be given by IV with the same dose and schedule. The PO levofloxacin is preferably administered 1 hour before or 2 hours after a meal, but may be taken with food if better tolerated by the patient. Antacids containing magnesium or aluminum, as well as sucralfate, metal cations such as iron, multivitamin preparations with zinc, and didanosine oral solution should not be taken within 2 hours before or after PO levofloxacin administration.

For children/adolescents who choose to take tablets of levofloxacin, the dose should be rounded to the nearest multiple of 125 mg. Rounding 'down' is permitted as long as the delivered dose i≥ 90% of the calculated dose. Otherwise, the dose should be rounded 'up' to the next multiple of 125 mg. For children using the oral solution, doses should be rounded to the nearest 25 mg.

If vomiting occurs within 30 minutes of taking the dose, the dose may be repeated once. If a dose is missed, it should be taken immediately and only if there are at least 12 hours until the next scheduled dose.

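### Section 4.2's tablet rounding rule has a 90% floor but no percentage ceiling, so within 13.9–75 kg tablets can deliver up to about 180% of the calculated dose

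*Combined protocol and SAP*

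**What the plan says.** Protocol Section 4.2 (Study Therapy) doses by weight and age. Under age 5 the instruction is "administer 10 mg/kg twice daily for a total of 20 mg/kg per day", with "Maximum: 250 mg per dose; 500 mg per day". From age 5 it is 10 mg/kg once daily, with "Maximum: 750 mg per day".

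Three consecutive sentences govern tablets:

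- The first, for patients who opt for tablets, says that "the dose should be rounded to the nearest multiple of 125 mg".
- The second sets the floor: "Rounding 'down' is permitted as long as the delivered dose" reaches 90% or more of the calculated amount.
- The third covers every other case: "Otherwise, the dose should be rounded 'up' to the next multiple of 125 mg".

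Tablets are the patient's choice, and no minimum weight or age is set for them. The alternative oral form has a finer step: "For children using the oral solution, doses should be rounded to the nearest 25 mg". IV is for patients who do not tolerate oral dosing.

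Section 5.0 halves the dose to 5 mg/kg (every 12 or 24 hours by age) at a creatinine clearance of 20–50 and says nothing about rounding. Both therapy delivery maps in Section 4.2 send the reader to that section for rounding of oral doses and repeat the daily maxima.

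**The concern.** The rule protects against underdosing by more than 10% but sets no matching limit on overdosing. A 125 mg step is coarse for a small child. When one tablet step falls just short of 90%, the only permitted move is to the next step, which at the lowest weights doubles the dose. The absolute maxima are the only upper limits, and they were not set in proportion to weight.

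The reference to the nearest multiple adds an ambiguity. In some weight bands the nearest multiple delivers less than 90%, so a site that stops at the first sentence and a site that reads all three give the same child different doses.

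At stake are dosing safety and consistency within Arm B. Levofloxacin safety is a stated objective (Section 1.2.4), and prophylaxis can run to Day 60, so an avoidable excess over the stated mg/kg is worth removing.

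**Working it through.** The plan states no figure for delivered dose as a share of calculated dose, so there is none to reproduce. The check applies the printed rule directly.

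**Inputs (Sections 4.2 and 5.0).** Full dose d = 10W mg per dose, where W is weight in kg, capped at 250 mg under age 5 and 750 mg from age 5. Half dose d = 5W. Tablet step 125 mg. Floor 90%.

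**One-rule reading.** Let k be the largest non-zero multiple of 125 not above d. Give k if k ≥ 0.9d; otherwise give k + 125.

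**Nearest-only reading.** Give the non-zero multiple of 125 closest to d.

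**Window.** 13.9 to 75 kg. The lower end is where 125 mg first fails the floor (125/0.9 = 138.9 mg). The upper end is where the 750 mg maximum is reached.

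**Where the overshoot peaks.** It is largest just above d = 125m/0.9, where the dose jumps to 125(m+1). The ratio there is 0.9(m+1)/m:

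- m = 1: 1.80 (13.9 kg)
- m = 2: 1.35 (27.8 kg)
- m = 3: 1.20 (41.7 kg)
- m = 4: 1.125 (55.6 kg)

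**Where it exceeds 125%.** The rounded-up dose is 125% or less once d ≥ 100(m+1). For m = 1 that is 200 mg, so the band runs from 13.9 to just below 20.0 kg. For m = 2 it is 300 mg, so the band runs from 27.8 to just below 30.0 kg. The second band exists only from age 5, because under 5 the calculated dose is capped at 250 mg. For m = 3 or more the peak is already at or below 120%.

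| Weight (kg) | Calculated (mg) | One rule: dose (%) | Nearest only: dose (%) |
|---|---|---|---|
| 13.8 | 138 | 125 (90.6) | 125 (90.6) |
| 13.9 | 139 | 250 (179.9) | 125 (89.9) |
| 14 | 140 | 250 (178.6) | 125 (89.3) |
| 18.7 | 187 | 250 (133.7) | 125 (66.8) |
| 18.8 | 188 | 250 (133.0) | 250 (133.0) |
| 20 | 200 | 250 (125.0) | 250 (125.0) |
| 27.8, from age 5 | 278 | 375 (134.9) | 250 (89.9) |
| 41.7, from age 5 | 417 | 500 (119.9) | 375 (89.9) |
| 55.6, from age 5 | 556 | 625 (112.4) | 500 (89.9) |

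**Do the maxima help?** At 14 kg under age 5, 250 mg twice daily meets the 250 mg and 500 mg limits exactly and gives 500/14 = 35.7 mg/kg/day against 20. From age 5 at the same weight it is 250/14 = 17.9 mg/kg once daily against 10.

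**Where nearest and floor disagree (full dose).** The bands are 13.9–18.7 kg at any age, and 27.8–31.2, 41.7–43.7 and 55.6–56.2 kg from age 5. At 68.75–69.4 kg two doses are allowable: at 69 kg, 750 mg is nearest (108.7%), but rounding down to 625 mg (90.6%) is permitted. Nearest-only ranges from 67% just below 18.75 kg to 133% at 18.75 kg (250/187.5).

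**Oral solution.** Rounding to 25 mg gives 92–108% of the full dose over the same window. At 14 kg it gives 150/140 = 107%.

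**Secondary check, renal half dose.** If Section 4.2 rounding is carried into Section 5.0, 13.9 kg gives 69.5 mg, rounded to 125 mg = 8.99 mg/kg under either reading. At 27.8 kg, 139 mg becomes 250 mg = 8.99 mg/kg under the one-rule reading and 125 mg = 4.5 mg/kg under nearest-only. The peak in the window is 5 × 1.8 = 9.0 mg/kg. Solution gives 86–114% of the half dose.

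**The case against.** **Self-contradiction.** A reader might infer that the three tablet sentences flatly contradict each other. The documents do not require that. The second and third sentences naturally qualify the first: aim for the nearest multiple, go down only above the floor, otherwise go up. That objection stands, and the analysis uses that reading as its main one. It does not rescue the rule, because that is the reading that reaches about 180%. Nearest-only avoids this at the price of delivering as little as 67%, below the printed floor.

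**No upper limit at all.** A reader might also infer this. It is not so: Section 4.2 and both delivery maps print absolute maxima. What is missing is a limit in proportion to the calculated dose.

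**180% as the overall maximum.** It is the peak only within 13.9–75 kg. Enrolment starts at 6 months, and a 6 kg child given one 125 mg tablet step would receive 208%. Children that small would probably take solution, but that is an assumption.

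**Narrow scope.** Only patients who choose tablets are affected; above 30 kg the full dose never exceeds 125%. From age 5, even 17.9 mg/kg/day is below the 20 mg/kg/day that the protocol gives younger children. This limits the concern, mainly to tablet takers under 5 at 13.9–20 kg, but does not show that the excess is safe. The delivery maps also record calculated and administered doses side by side, so a large gap would be visible. They do not tell the site to act on it.

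**Renal dose.** A reader might take the loss of the renal reduction as an established defect. It is an inference. Section 5.0 prints mg/kg doses only, entry requires a GFR above 70 or an age-based creatinine limit, and clearance would have to fall on study. It belongs in a secondary note.

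**Conclusion.** The concern holds as a missing percentage ceiling. Read as one rule, and within 13.9–75 kg, Section 4.2 delivers more than 125% of the calculated full dose from 13.9 to just below 20.0 kg at any age and from 27.8 to just below 30.0 kg from age 5. The peak is about 180% at 13.9 kg, and the absolute maxima do not prevent it. The reference to the nearest multiple is a lesser fault: it leaves room for a two-fold difference between sites at 14 kg.

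The result rests only on the printed doses, step, floor and maxima. It applies to tablet takers, whose number the documents do not give. No sample size or power figure is affected, and nothing in the documents supports inferring an effect on the bacteremia endpoint.

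The renal figure of up to 9.0 mg/kg against 5 is conditional on Section 4.2 rounding being meant to apply to Section 5.0. This is a correction that should be made; it does not call the design into question.

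**What to change.** Replace the three tablet sentences in Section 4.2 with one rule:

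> Use the 125 mg multiple closest to the calculated dose that delivers 90% to 125% of it within the stated maxima; on a tie, use the lower. If none exists, use oral solution rounded to the nearest 25 mg.

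Keep IV, as now, for patients who do not tolerate oral dosing. The 125% limit has no source in the documents; it is a proposed value for the sponsor to confirm. The 90–125% limits should apply to tablets only, since solution at the half dose can fall to 86%.

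Add one sentence to Section 5.0 saying that the same tablet limits apply to the reduced doses. A weight table on both delivery maps would help:

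- Full dose from age 5: 125 mg at 10.0–13.8 kg; 250 mg at 20.0–27.7; 375 mg at 30.0–41.6; 500 mg at 41.7–55.5; 625 mg at 55.6–68.7; 750 mg from 68.8. No tablet below 10.0 or at 13.9–19.9 and 27.8–29.9 kg.
- Full dose under 5, per dose: 125 mg at 10.0–13.8 kg; 250 mg from 20.0. No tablet below 10.0 or at 13.9–19.9 kg.
- Half dose, up to 75 kg: 125 mg at 20.0–27.7 kg; 250 mg at 40.0–55.5; 375 mg from 60.0. No tablet below 20.0 or at 27.8–39.9 and 55.6–59.9 kg.

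The cost is a wording change and a short table. The downside is that tablet takers in the gaps must use solution. The protocol already provides it, but some children may accept it less readily, and Section 2.2 notes compliance problems in earlier pediatric prophylaxis studies.
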